### 5.3.3 Screening and Baseline Procedures

The following procedures are performed on or the day before the first planned administration day.

- Review and signature of informed consent form
- The following evaluations are required only if RDEB diagnosis documentation is not available to support entry into this protocol. If these are needed, the screening visit may occur several weeks prior to the baseline visit:
  - Collection of a biopsy for EM/IEM
  - Collection of a biopsy for IF
  - Collection of blood for genetic testing
- Collection of demographic data (e.g. sex, age, race, and ethnicity)
- Inclusion/exclusion criteria
- Medical history and medication history
- Collection of blood (approximately 15 mL) for clinical laboratory tests:
  - Serum chemistry
  - Hematology
  - HIV, Hep B, Hep C
  - Baseline viral shedding
  - Baseline HSV and COLVII autoantibodies
- Collection of urine
  - For a pregnancy test, if applicable
  - For baseline viral shedding
- Physical and skin exam
- Vital signs: blood pressure, heart rate, respiratory rate, temperature
- Collection of a baseline skin swab for viral shedding analysis
- Bacterial culturing of target wounds (if clinical evaluation is indicative of infection)
- Digital imaging of target areas
- Collection of a biopsy from intact skin for IF and IEM analyses. This collection can occur at a later visit at the discretion of the Investigator.
- Patient reported outcomes (PRO) questionnaire
- Investigator's global assessment

## 5.4 Cycle 1

The patient will visit the Investigative site for the first dose of Cycle 1. Additional Cycle 1 doses can occur on-site or at-home at the discretion of the Investigator. Unless the patient requires disease characterization, Day 1 of Cycle 1 is the same day as the Screening/Baseline visit. For Cycle 1, KB103 and placebo are administered topically every 2 to 3 days to correspond with bandage changes, up to 3 months.

### 5.4.1 On-Site Dosing Day Procedures

For visits that occur at the clinic, the following procedures may be performed:

- Adverse events
- Concomitant medications
- Vital signs
- Viral shedding skin swab collection
- Digital imaging of target wound areas
- PRO assessment
- Investigator's global assessment
- Wound stenciling
- Topical administration of KB103 and placebo to the target areas

### 5.4.2 At-home Procedures

After the first administration of each cycle, KB103 may be administered at home by a caretaker every 2 to 3 days until wound closure, a stopping criterion is met, 3 months have elapsed, or until directed to discontinue by the Investigator.

Appendix 1 provides administration instructions. Wound closure is monitored through remote imaging.

### 5.4.3 Last Dosing Day of Cycle 1

The patient will visit the Investigative site on or near the final Cycle 1 administration day, in which the following procedures will be performed:

- Collection of blood (approximately 10 mL) for clinical laboratory tests:
  - Serum chemistry
  - Hematology
  - Viral shedding
  - HSV and COLVII autoantibodies
- Collection of urine for viral shedding
- Optional: biopsy collection from a wound area
- Wound stenciling
- Topical administration of KB103 and placebo to the target areas

## 5.5 Observation Period (OP) 1

Following Cycle 1 wound closure and/or 3 months, the patient returns home. Wound areas are imaged every 2 to 3 days at home with a phone app.

The duration of OP 1 varies. If complete wound closure is obtained during Cycle 1, OP 1 ends when the wound(s) re-open. If complete closure is not obtained during Cycle 1, OP 1 ends when the wound surface area increases relative to size of the wound at the last Cycle 1 administration.

## 5.6 Cycle 2

The patient will visit the Investigative site for the first dose of Cycle 2. Additional Cycle 2 doses can occur on-site or at-home at the discretion of the Investigator. For Cycle 2, KB103 and placebo are administered topically every 2 to 3 days to correspond with bandage changes, up to 3 months.

### 5.6.1 On-site Dosing Day Procedures

For visits that occur at the clinic, the following procedures may be performed:

- Adverse events
- Concomitant medications
- Vital signs
- Viral shedding skin swab collection
- Digital imaging of target wound areas
- PRO assessment
- Investigator's global assessment
- Wound stenciling
- Topical administration of KB103 and placebo to the target areas

### 5.6.2 At-home Procedures

After the first administration of each cycle, KB103 may be administered at home by a caretaker every 2 to 3 days until wound closure, a stopping criterion is met, 3 months have elapsed, or until directed to discontinue by the Investigator.

Appendix 1 provides administration instructions. Wound closure is monitored through remote imaging.

### 5.6.3 Last Dosing Day of Cycle 2

In addition to the procedures above, the following additional procedures should occur on or near the final Cycle 1 administration day:

- Collection of blood (approximately 10 mL) for clinical laboratory tests:
  - Serum chemistry
  - Hematology
  - Viral shedding
  - HSV and COLVII autoantibodies

- Collection of urine for viral shedding
- Optional: biopsy collection from a wound area
- Wound stenciling
- Topical administration of KB103 and placebo to the target areas

## 5.7 Observation Period (OP) 2

Following Cycle 2 wound closure and/or 3 months, wound areas are imaged remotely every 2 to 3 days at home with a phone app.

OP 2 also consists of monthly visits to the clinic.

### 5.7.1 OP 2 Monthly Visits

At 30-day intervals (+/- 7 days) after the last administration of Cycle 2, the patient returns to the clinic for follow-up procedures:

- Adverse events
- Concomitant medications
- Vital signs
- Digital imaging of wounds
- PRO assessment
- Investigator's global assessment
- Collection of blood (approximately 10 mL) for clinical laboratory tests:
  - Serum chemistry
  - Hematology
  - Viral shedding
  - HSV and COLVII autoantibodies
- Collection of a skin swab for viral shedding analysis
- Collection of urine for viral shedding
- Month 3 only: physical exam
- Optional: Biopsy from a wound administered KB103 or placebo
- Wound stenciling
- If a target wound is open: Topical administration of KB103 and placebo to the target areas.

## 5.8 Unscheduled Visits

Subjects may visit the clinic for unscheduled visits as deemed appropriate by the Investigator. Any or all of the monthly visit procedures may be performed during unscheduled visits.

## 5.9 Long-Term Follow-Up Period

Upon completion of the End of Study / Early Termination Visit, subjects will enter into a Long-Term Follow-Up Period.

At a minimum, subjects will be contacted yearly for at least 5 years. Subjects will be contacted by phone. In addition, the subject's primary care provider will be asked to contact the Investigator regarding any unexpected or serious adverse events. Telephone contact reports will document the discussions and the information obtained will be captured on case report forms. The following activities will occur at the one-year follow-up intervals:

- Recording of exposures to mutagenic agents and other medicinal products
- Recording of any new serious adverse events, hospitalizations, or illnesses (including new malignancies, new incidence or exacerbation of a pre-existing neurologic disorder, new incidence or exacerbation of a prior rheumatologic or other autoimmune disorder, new incidence of a hematologic disorder).
- Discussion with primary care provider regarding medication and medical history.
- If a skin cancer occurs in the region of the KB103 administration, attempts will be made to collect samples of the skin cancer to evaluate cells for the presence of viral vector.

## 6      **Investigational Product**

Subjects are administered topical KB103 to one or two wound areas, and topical placebo to a second wound area. Wound areas have a surface area of up to 50 cm^2.

During Cycles 1 and 2, topical KB103 and placebo are administered every two to three days to coincide with bandage changes. Administrations continue until the wound closes, a stopping criterion occurs or at the discretion of the Investigator, not to exceed 3 months per cycle. After the first administration of each cycle, administrations can be administered at home by a trained caretaker at the discretion of the Investigator. These are referred to as "At-Home Topical Administrations" below. During visits to the Investigative site, KB103 may be administered topically by the Investigator. KB103 is prepared according to the pharmacy manual prior to administration.

### **6.1      At-Home Topical Administrations**

At the discretion of the Investigator, KB103 may be administered at home. The Investigator will use at-home imaging to make remote dosing decisions, for example, if at-home dosing should discontinue due to wound closure.

Trained caretakers may administer KB103 or trained personnel may travel to the subject to administer KB103. Training will be documented and will consist of administration, containment, and disposal procedures. At-home administration and disposal instructions are provided to the subjects and are in Appendix 1.

### **6.2      Dose Level**

Each topical KB103 dose is 6e8 PFU per wound area per day.

### **6.3      Wound Area Selection**

Up to three wound areas are selected to be part of the study: one or two to receive KB103, and one to receive placebo. Final selection of the wound areas occurs at baseline. The following is considered when selecting target wound areas:

- **Wound areas can consist of one wound, or multiple wounds, and can include intact skin.**
- **The size of the wound area.** Target wound areas have a surface area up to 50 cm^2.
- **The location of the wound area.** Appropriate sites are on the anterior and/or lateral trunk and/or upper and/or lower extremities in areas protected from frequent trauma or injury. Excluded areas include the face, and areas close to mucous membranes (genitourinary, oral or anal mucosa).

- **The appearance of the wound.** Wounds should appear clean with adequate granulation tissue, excellent vascularization, and not appear infected.
- **Historical consistency in size of the wound.** A wound with a historically more consistent surface area is chosen over a less consistently sized wound.
- **The similarity of the wounds.** To the extent possible, similarity in location on the body should be considered.
- Wounds that have previously been administered investigational gene or cell therapy (except for previous KB103 administration) are not eligible for KB103 and placebo administration.

The Investigator will first selection two areas; one for KB103 and one for placebo. If another area meets the criteria above, it will be considered for inclusion in the study to receive KB103.

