## 1.6 Rationale for Protocol Amendments

Four subjects were enrolled onto version 2 of the Phase 2 portion of the protocol. Three subjects (1 adult and 2 children) were administered 3e8 per wound daily for 5 days. One adult was administered 6e8 daily for 5 days. There were no signs of immunogenicity, no KB103-related adverse events and the data indicate that 3e8 per wound per administration was an effective dose for wounds 20 cm^2 or less.

Post-dose imaging from these patients clearly indicated that wound morphology and size is a major factor in wound healing as a result of KB103 administration. Wounds that were chronic but recurring based on natural history tended to heal and close completely within 7 to 10 days of KB103 administration. Chronic wounds that were open for a few years showed signs of healing following an initial five consecutive applications but the wound healing process appears to stagnate. These wounds would likely benefit from additional administrations to obtain full closure. Caregivers of the patients currently on trial have requested additional administrations to wounds that have clearly benefited but have not achieved complete wound closure.

Therefore, version 3.1 of the protocol incorporated dosing every 2 to 3 days for two weeks at 2e8 PFU with the option of at-home KB103 administrations, at the discretion of the Investigator.

Five patients were enrolled onto version 3.1 of the protocol. KB103 continues to be well tolerated and wound healing is observed in KB103 administered wounds. Wound healing results of the KB103 treated wounds evaluated to-date continues to show improvement. There is also empirical evidence that repeat administration on the chronic wounds that were retreated in patients that rolled over from the previous portion of the study showed improved healing with complete closure of the wound observed. Therefore, version 4.0 incorporates a 2-cycle approach to KB103 administration with greater flexibility given regarding the number of administrations within each cycle to understand the duration of treatment prior to moving into the Phase 3 Clinical trial.

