### 10.5.3 Target Wound Area

Target wound surface area is obtained through on-site and at-home imaging of target areas. Change in area from baseline is evaluated for using a paired t-test for each KB103 target wound vs. control wound.

Time to closure and durability of closure will be assessed after each cycle of administrations.

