- The analysis performed in Section 8.1.1 for the efficacy objective will be repeated for weeks 8, 10 and 12, separately with and without stratification by time points for observed, PP and LOCF imputed ITT populations.

Other Analyses of the Change in Wound Surface Area for observed and LOCF imputed populations Include:

- The analysis performed in Section 8.1.1 for the efficacy objective will be repeated for wound healing with $\geq 50\%$ reduction in wound surface from baseline with and without stratification by time points.
- The analysis performed in Section 8.1.1 for the efficacy objective will be repeated for wound healing with $\geq 75\%$ reduction in wound surface from baseline with and without stratification by time points.

- The analysis performed in Section 8.1.1 for the efficacy objective will be repeated for wound healing with 100% reduction in wound surface with and without stratification by time points.

All the efficacy wound healing responses will be summarized by treatment and timepoints for observed and LOCF imputed ITT populations. The percent reduction in wound surface from baseline will be summarized descriptively by treatment and timepoints and treatment comparisons will be performed using the Wilcoxon rank-sum test for observed and LOCF imputed ITT populations. A subject listing will be provided for these reductions in wound surface.

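### KB103 and placebo areas are matched on body location only, although the protocol itself names wound morphology and size as a major factor in healing; the cost is avoidable noise and chance imbalance

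*Protocol*

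**What the plan says.** **Selection (protocol 6.3).** The criterion headed as similarity of the wounds reads: "To the extent possible, similarity in location on the body should be considered". The other criteria apply to each area on its own: a cap of 50 cm² per area, permitted sites, clean appearance, and a preference for stability ("A wound with a historically more consistent surface area is chosen over a less consistently sized wound"). An area may hold one or several wounds and may include intact skin, so the cap does not make the open wound area of two areas similar.

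**Prognosis (protocol 1.6).** Four subjects treated under version 2 led the sponsor to conclude that "wound morphology and size is a major factor in wound healing as a result of KB103 administration". Recurring wounds "tended to heal and close completely within 7 to 10 days of KB103 administration". For the others, "Chronic wounds that were open for a few years showed signs of healing", after which healing is said to have stalled.

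**Baseline data (protocol 5.3.3).** Imaging of the target areas is listed. Wound type and time open per area are not.

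**Analysis.** Protocol 10.5.3: "Change in area from baseline is evaluated for using a paired t-test for each KB103 target wound vs. control wound". In the SAP, section 8.1.1 uses a CMH test stratified by week. Section 8.1.1.1 compares percent reduction between treatments: "treatment comparisons will be performed using the Wilcoxon rank-sum test for observed and LOCF imputed ITT populations". Sections 8.1.2 and 8.1.3 use analysis of variance with treatment as the only effect.

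**Allocation.** Protocol 6.3 has the Investigator pick one area for KB103 and one for placebo, and 6.5 has the control area chosen at baseline. The available v4.0 text describes no randomisation of areas. Protocol 1.5 says wounds were randomised under version 1.0. SAP sections 3 and 8 describe the whole Phase I/II programme as randomised, and SAP section 1 says it is not blinded.

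**The concern.** The placebo wound is meant to show what the KB103 wound would have done without KB103. That works best when the two wounds share the features that drive healing. The sponsor has named such features and reported a sharp contrast between recurring and long-open wounds, yet the selection rule pairs areas on something else. If one member of a pair is small and recurring and the other large and long open, their difference mixes wound type with treatment.

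With 3 subjects in this version and 12 to 14 overall, a few unlike pairs need not cancel out. The result would be a less precise contrast and a real chance that one treatment holds the easier wounds. Section 1.6 says this version is meant to inform Phase 3, so a contrast blurred by wound type would carry forward.

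**Working it through.** The documents give no sample-size calculation, standard deviation or closure rates by wound type, so there is no figure to reproduce. The closure rates, wound areas, correlation and selection probabilities below are assumptions. The subject counts come from the documents.

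**1. What each planned test accounts for**

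| Test | Paired within subject | Scaled to own baseline | Baseline area as covariate | Wound type |
|---|---|---|---|---|
| Protocol 10.5.3, t-test on change in area | yes | no | no | no |
| SAP 8.1.1, CMH on ≥90% reduction | no (strata are weeks) | yes | no | no |
| SAP 8.1.1.1, rank-sum on percent reduction | no | yes | no | no |
| SAP 8.1.2 and 8.1.3, ANOVA on time to and duration of closure | no | yes (threshold) | no | no |

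**2. Size on the unscaled measure.** Suppose KB103 has no effect and both wounds heal by the same fraction f. The pair difference in area change is then f × (larger baseline − smaller baseline). With f = 0.5:
- 25 vs 20 cm²: 0.5 × 5 = 2.5 cm²
- 40 vs 10 cm²: 0.5 × 30 = 15 cm²
- 50 vs 5 cm²: 0.5 × 45 = 22.5 cm²

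On the percent scale all three differences are zero.

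**3. Noise from type.** Assume no drug effect, closure probability 0.8 for recurring and 0.2 for long-open wounds, an equal mix, and independent types within a subject.
- Unmatched pair: each wound closes with probability 0.5, so the variance of the pair difference is 2 × 0.5 × 0.5 = 0.50.
- Type-matched pair: 2 × 0.8 × 0.2 = 0.32.
- 12 pairs, none matched: SE = √(0.50/12) = 0.204.

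**4. How many pairs a new rule can reach.** By the table in SAP section 3, 2 + 4 + 5 = 11 subjects precede v4.0. Version 4.0 plans 3 more, which gives 14, the ceiling in the protocol synopsis. The SAP elsewhere counts 12.
- 3 of 12 matched: √[(9 × 0.50 + 3 × 0.32)/144] = √(5.46/144) = 0.195, 5% below 0.204.
- 3 of 14 matched: √[(11 × 0.50 + 3 × 0.32)/196] = 0.182, against √(0.50/14) = 0.189, 4% lower.
- 1 of 12 matched: √[(11 × 0.50 + 0.32)/144] = 0.201, 1.5% below 0.204.

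Sensitivity with 3 of 12 matched:
- At 0.7/0.3 the matched variance is 2 × 0.7 × 0.3 = 0.42, and the SE is √[(9 × 0.50 + 3 × 0.42)/144] = 0.200, 2% below 0.204.
- At 0.9/0.3 the unmatched variance is 2 × 0.6 × 0.4 = 0.48 and the matched variance is (0.18 + 0.42)/2 = 0.30. The SE is √[(9 × 0.48 + 3 × 0.30)/144] = 0.190, against √(0.48/12) = 0.200, 5% lower.

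**5. Chance imbalance and bias.** If the gap between types is the same in both arms, a 10-point excess of recurring wounds in one arm shifts the closure difference by 0.4 × 10 = 4 points (at 0.7/0.3) to 0.6 × 10 = 6 points (at 0.8/0.2 or 0.9/0.3). With 3 unlike pairs and random allocation, the chance that all three favour KB103 is 0.5³ = 0.125.

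Whether this is bias depends on allocation. A simulation (40,000 runs, no drug effect, within-pair correlation 0.5, half the pairs unlike, prognostic gap 1 SD, one-sided 5% paired t-test) gave:

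| Share of unlike pairs with the better wound on KB103 | Type I error, n = 12 | Type I error, n = 3 |
|---|---|---|
| 50% (random) | 0.05 | 0.05 |
| 60% | 0.08 | 0.06 |
| 75% | 0.17 | 0.09 |
| 100% | 0.42 | 0.14 |

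Under random allocation the error rate holds, but the SD of the pair difference rises from 1.00 to √(1 + 0.5 × 1²) = 1.22.

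**The case against.** Several points on the other side stand.

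*Bias does not follow from lack of matching.* A reader might infer that the contrast is tilted towards KB103. That needs non-random allocation, and the documents conflict on whether areas are randomised. Nothing in them shows that better wounds were steered to KB103.

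*The benefit is easily overstated.* Matching all 12 pairs would cut the standard error by 20% (√(0.32/12) = 0.163 against 0.204). That gain is out of reach, because a change to section 6.3 cannot re-pair subjects already treated. If a subject's wounds tend to be of one type, the gain shrinks further.

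*Size is not ignored.* The SAP's healing endpoints are defined against each wound's own baseline, and the preference for historically stable wounds narrows variation somewhat. Scaling does not remove differences in prognosis by size, and it does nothing for type.

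*Section 1.6 describes KB103-treated wounds.* It gives no placebo healing rates by type, so an equal gap in both arms is an assumption. It also reports complete closure of long-standing wounds on retreatment, and v4.0 doses differently from version 2, so the contrast may be weaker now. Even so, if response to KB103 depends on type, an unlike pair still confuses type with treatment.

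*Wound type may be captured somewhere.* The case report form is not among the documents. One can say only that section 5.3.3 does not list it.

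**Conclusion.** The point holds as one of precision and chance imbalance. The protocol names morphology and size as a major factor in healing and contrasts recurring with long-open wounds, but matches on location alone. No planned test accounts for wound type, and the protocol's own t-test is not even scaled to baseline area.

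The gain from matching alone is modest: at most about 5% off the standard error (0.204 to 0.195), and 1.5% if only one subject remains to be matched. Both figures rest on assumed closure rates of 0.8 and 0.2 and independent wound types. The analysis change reaches every subject. Where paired areas differ in size, the unscaled t-test can show a sizeable difference with no drug effect, 15 cm² in the 40 vs 10 cm² illustration.

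Systematic bias is conditional on how areas are allocated. The protocol and SAP must be reconciled on that before anyone can say whether it is present.

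**What to change.** 1. **Protocol 6.3.** Require the first KB103 area and the placebo area to be chosen as a pair, as alike as feasible in baseline open wound area and in type (recurring versus continuously open), as well as in location. Record type and time open at baseline for the target wound or wounds in each area; where an area holds several wounds, record them by wound.
2. **Allocation.** State whether areas are randomised within subject, and make protocol 6.3 and 6.5 agree with SAP sections 3 and 8.
3. **Area-change analysis, all subjects.** Replace the unscaled t-test and the unpaired rank-sum test with a within-subject analysis on the percent or log-ratio scale, with the pair's difference in log baseline area as covariate. If the log ratio is used, say how a fully closed wound (area zero) is handled. State how a second KB103 area enters, so that one placebo wound is not counted as two independent controls.
4. **Same-type pairs.** Label any analysis restricted to them as exploratory. For subjects already treated, type would be assigned from history, in an unblinded study that has already been partly analysed.

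The cost is a sentence in 6.3, one or two CRF fields, SAP wording, one degree of freedom (with 12 pairs, 10 residual instead of 11) and a slightly narrower choice of areas. With 3 subjects alone the covariate model would leave 1 degree of freedom, so it should be fitted across all subjects.
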